1.3. Clinical Experience

Insys Development Company, Inc. has studied the pharmacokinetics, efficacy, safety, and tolerability of fentanyl sublingual spray in 7 clinical studies (5 pharmacokinetic, and 2 efficacy and safety studies). Overall, in the clinical trial program for the 7 completed trials, 98 healthy adult volunteers and 377 adults with cancer were exposed to fentanyl sublingual spray. In

addition, two trials in opioid naïve subjects have recently been completed. Study INS-15-049 was a Phase 1, open-label, randomized, single ascending dose study in 50 opioid naïve subjects at a single study center designed to assess the safety, tolerability, pharmacokinetics, and pharmacodynamics of a single dose of fentanyl sublingual spray or fentanyl citrate IV. Study INS002-15-050 was a Phase 1, multiple ascending dose study (INS002-15-050) in 96 opioid naïve subjects at one study site designed to assess the pharmacokinetics (PK), pharmacodynamics (PD), safety, and tolerability of multiples doses of SUBSYS® (fentanyl sublingual spray) or fentanyl citrate IV.

In FNY-P4-270, fentanyl sublingual spray doses of 100 µg, 400 µg, and 800 µg were associated with well-defined, mainly proportional pharmacokinetics. INS-06-003 characterized the pharmacokinetic profile and comparative bioavailability of fentanyl administered by 3 routes: intravenously (100 µg) and via 2 transmucosal delivery systems - OTFC (a lozenge containing 400 µg of fentanyl) and fentanyl sublingual spray 400 µg.¹⁵ INS-06-004 determined the pharmacokinetics of 5 different doses (100, 200, 400, 600, and 800 µg) of fentanyl sublingual spray and investigated the impact of temperature (cold or hot beverage) and pH (oral bicarbonate or carbonate) in the oral cavity on the bioavailability of fentanyl sublingual spray.²¹ INS-09-011 assessed the effect of oral mucositis on the absorption and distribution of fentanyl when administered as a sublingual spray in patients with cancer pain. No serious AEs were reported during these 4 pharmacokinetic studies. Another pharmacokinetic study, INS-13-019, compared the bioavailability of fentanyl sublingual spray versus IM fentanyl citrate. INS-05-001, a phase 3 study, demonstrated that fentanyl sublingual spray was well tolerated and efficacious in reducing breakthrough cancer pain, with a rapid onset of action.¹⁶ Long-term safety (90 days) of fentanyl sublingual spray in the management of patients with breakthrough cancer pain was assessed in INS-06-007.

In INS002-15-049, pharmacokinetic analyses showed that mean concentrations and mean exposure parameters of fentanyl increased with increasing doses of fentanyl sublingual spray ranging from 100 to 800 µg. Mean maximum plasma concentrations were reached between 0.27 and 0.60 hours post-dose for fentanyl sublingual spray. Single dose administration of fentanyl sublingual spray at doses ranging from 100 to 800 µg was generally well tolerated in opioid naïve subjects. No SAEs were observed in the study. The most frequently reported AEs were consistent with the safety profile of fentanyl when administered in other forms, and included somnolence, nausea, and vomiting. There were no clinically relevant differences among treatment groups in AEs reported during this clinical trial. The analysis of the results of INS002-15-050 is currently ongoing.

In INS002-15-050, multiple ascending doses were studied and demonstrated that most doses were well-tolerated and that doses up to 400 µg every 4 hours were safe and well-tolerated.

1.4. Dose Selection Rationale

For this study, the total daily doses of 600 µg and 1200 µg fentanyl were selected for this trial based on the observations from the multi-dose study to be well within the margin of safety. These doses are supported by nonclinical pharmacodynamics, pharmacokinetic, efficacy, and safety studies, and the results of the completed Insys Phase 1 studies (INS002-15-049 and INS002-15-050).

1.5. Summary of Potential Risks and Benefits

Fentanyl has a well-known safety profile. Risks for study participants include those associated with the following:

- Fentanyl has side effects similar to other opioids, including vomiting, nausea, constipation, dyspnea, and somnolence.
- The bunionectomy procedure itself may include bleeding, infection, and neurologic injury.

The potential risks of study participation include those associated with exposure to Fentanyl Sublingual Spray and the risks of medical evaluation, including venipuncture. A summary of the pharmaceutical properties and known potential risks of Fentanyl Sublingual Spray is provided in the current version of the investigator's brochure (IB). The investigator must become familiar with all sections of the Fentanyl Sublingual Spray IB before the start of the study.

The potential benefits of study participation are the subjects undergoing bunionectomy may experience a reduction in postoperative pain as a result of treatment with Fentanyl Sublingual Spray and will understand that they are contributing to the scientific knowledge that may lead to expansion of the treatment options for patients with postoperative pain. No other benefits of participation are anticipated.

2. STUDY OBJECTIVES

2.1. Primary Objective

- To evaluate analgesic efficacy of Fentanyl Sublingual Spray compared with placebo in subjects with postoperative pain after a bunionectomy.

2.2. Secondary Objectives

- To evaluate the safety of Fentanyl Sublingual Spray compared with placebo in subjects with moderate to severe postoperative pain after a bunionectomy.
- To evaluate the time to onset of analgesia for Fentanyl Sublingual Spray.

3. INVESTIGATIONAL PLAN

3.1. Overall Study Design

This is a Phase 2 multicenter, randomized, double blind, multiple dose, parallel group, and placebo controlled study to evaluate the safety and efficacy of up to 2 dosing regimens of Fentanyl Sublingual Spray (100 µg q4h or 200 µg q4h) and/or matching placebo in subjects with moderate to severe postoperative pain after a bunionectomy.

The study will comprise 4 periods: Screening Period (Days -28 to -1), Surgical Period (Day 0), Treatment Period (48 hours; Days 1 to 3), and Follow-up Period (Day 7 ± 2 days). The study design is represented schematically in Figure 1.

Subjects will be admitted to the study site on the morning of the scheduled surgery (Day 0), will remain at the study site until Postoperative Day 3 (a total of 3 nights at the study site), and will return for the Follow up Visit on Day 7 ± 2 days (5 to 9 days after surgery).

During the Screening Period, subjects who meet all inclusion and no exclusion criteria will be eligible for enrollment. After providing written Informed Consent, subjects will undergo study specific screening procedures. Eligible subjects will complete all screening procedures within 28 days before the surgery (Days -28 to -1)

On Day 0, regional anesthesia will be established using a Popliteal Sciatic Nerve Block, using standardized techniques, after which subjects will undergo primary, unilateral, first metatarsal bunionectomy with osteotomy and internal fixation. When the regional anesthetic wears off and the subjects request pain medication, they will be asked to rate their pain intensity using an 11-point (0-10) Numeric Rating Scale (NRS). During the 9-hour period after discontinuation of the anesthetic block, subjects who experience a pain intensity rating of ≥ 4 on the NRS are eligible to be enrolled in the study. Pulse oximetry will be monitored continuously after the procedure as a safety measure.

During the Treatment Period, approximately 45 subjects will be randomly assigned to 1 of 3 treatment groups: Fentanyl Sublingual Spray 100 µg q4h, 200 µg q4h, or matching placebo.

An electrocardiogram (ECG) will be conducted after surgery but before the first dose of the study drug and serve as a baseline for comparison to subsequent tracings. The time of the NRS assessment before study drug administration is defined as Baseline; the time of administration of the first dose of study drug is defined as Time 0. Study drug will be provided by blinded study personnel in a predefined manner to ensure adequate blinding and appropriate dosing regimens for the active drug and placebo. Subjects should not have anything orally except room-temperature water within 15 minutes of each dose. The Treatment Period will continue through 48 hours after Time 0. Pulse oximetry will be continuously monitored and SpO₂ data will be recorded at select time points including baseline before first dose of study drug and 90 minutes and 12, 24, and 48 hours after Time 0. Additional ECGs will be performed at 90 minutes, 12 hours, 24 hours, and 48 hours after Time 0.

Ibuprofen 400 mg will be allowed orally every 4 to 6 hours as needed for rescue medication after study drug treatment has begun. If subjects are unable to tolerate 400 mg ibuprofen or if there is insufficient pain relief, 30 mg of ketorolac tromethamine (i.e., Toradol®) may be administered intravenously or intramuscularly every 6 to 8 hours as needed for pain. The total daily (24 hour)

dosage of ibuprofen medication should not exceed 2400 mg and ketorolac should not exceed 90 mg.

During the Treatment Period, subjects will be allowed to use assigned study medication for primary rescue medication no more frequently than 4 hours from previous study medication dose and no more than 6 times in a 24-hour period. Subjects will be encouraged to wait for at least 1 hour after the first dose of study drug before receiving rescue medication to allow time for the study drug to exert its pharmacologic effect.

During the Treatment Period, subjects whose pain cannot be adequately managed (in the investigator's opinion) by a combination of study drug and rescue medication, or who develop unacceptable side effects during the study, will be discontinued from further study participation. Their pain will be managed according to usual standard of care at the investigator's discretion.

Pain will be assessed on an 11-point Numeric Rating Scale (NRS) at Baseline before Time 0. Thereafter, subjects will rate their pain intensity (NRS) and pain relief (on a 5-point categorical scale) and record their assessments in an inpatient subject diary at scheduled times during the 48-hour period after Time 0 (at 2.5, 5, 15, 30, and 45 minutes, and 1, 1.5, 2, 3, 4, 5, 6, 7, 8, 12, 16, 20, 24, 32, 40, and 48 hours) and immediately before each use of each rescue analgesia during the Treatment Period. Time to perceptible and meaningful pain relief will be evaluated using the 2 stopwatch method (after the first dose only). Subjects will complete a subject's global evaluation of the study drug at the end of the Treatment Period (Day 3) before discharge from the study site.

[figure not shown]
If a subject discontinues the study prematurely, pain intensity, pain relief, and the subject's global satisfaction with study treatment should be assessed and recorded immediately before discontinuation.

Before discharge from the study site on Day 3, study personnel will dispense a prescription for outpatient pain medication (if not already dispensed) and subjects will be given an outpatient subject diary in which they will be instructed to record concomitant medications taken and adverse events (AEs) experienced after discharge. Subjects will also be instructed to return the outpatient subject diary to study personnel at the Follow up Visit, 7 ± 2 days after surgery.

The planned sequence and maximum duration of the study periods will be as follows:

- Screening Period: up to 28 days
- Surgical Period: Day 0
- Treatment Period: Days 1-3 (up to 9 hours post-surgery plus 48 hours of treatment and inpatient assessments)
- Follow-up: Day 7 ± 2 days (5 to 9 days after surgery) or early withdrawal

Subjects will be confined for approximately 72 hours at the study site for the Surgical and Treatment Periods. The maximum study duration for each subject is approximately 6 weeks

Figure 1: Study Design Schematic

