
Name of Active Ingredient: Fentanyl

Title of Study: A Phase 2 Multicenter, Randomized, Double-Blind, Multiple-Dose, Parallel-Group, Placebo-Controlled Study of Fentanyl Sublingual Spray for the Treatment of Moderate to Severe Post-Operative Pain

Indication: Moderate to severe post-operative pain

Objectives:
 
Primary: To evaluate analgesic efficacy of Fentanyl Sublingual Spray compared with placebo in subjects with postoperative pain after a bunionectomy.
 
Secondary:
 
 • To evaluate the safety of Fentanyl Sublingual Spray compared with placebo in subjects with moderate to severe postoperative pain after a bunionectomy. • To evaluate the time to onset of analgesia for Fentanyl Sublingual Spray. • To evaluate the time to rescue medication following administration of Fentanyl Sublingual Spray.

Methodology:
 
This is a Phase 2, multicenter, randomized, double blind, multiple dose, parallel group, and placebo controlled study to evaluate the safety and efficacy of up to 2 dosing regimens of Fentanyl Sublingual Spray (100 µg every 4 hours [q4h] or 200 µg q4h) and/or matching placebo in subjects with moderate to severe postoperative pain after a bunionectomy.
 
The study will comprise 4 periods: Screening Period (Days -28 to -1), Surgical Period (Day 0), Treatment Period (48 hours; Days 1 to 3), and Follow-up Period (Day 7 ± 2 days).
 
Subjects will be admitted to the study site on the morning of the scheduled surgery (Day 0), will remain at the study site until Postoperative Day 3 (a total of 3 nights at the study site), and will return for the Follow up Visit on Day 7 ± 2 day (5 to 9 days after surgery).
 
During the Screening Period, subjects who meet all inclusion and no exclusion criteria will be eligible for enrollment. After providing written Informed Consent, subjects will undergo study specific screening procedures. Eligible subjects will complete all screening procedures within 28 days before the surgery (Days-28 to -1)
 
On Day 0, regional anesthesia will be established using a Popliteal Sciatic Nerve block, using standardized techniques, after which subjects will undergo primary, unilateral, first metatarsal bunionectomy with osteotomy and internal fixation. When the regional anesthetic wears off and the

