4. TREATMENTS

4.1. Treatments Administered

Eligible subjects meeting all study entry criteria will be randomly allocated in a 1:1:1 ratio to one of the following treatments containing active or placebo administered up to 6 doses per day as shown in the table below:

Table 1: Study Treatment Regimens

Treatment group	Day 1						Day 2					
	Dose 1	Dose 2	Dose 3	Dose 4	Dose 5	Dose 6	Dose 1	Dose 2	Dose 3	Dose 4	Dose 5	Dose 6
100 µg	100 µg	100 µg	100 µg	100 µg	100 µg	100 µg	100 µg	100 µg	100 µg	100 µg	100 µg	100 µg
200 µg	200 µg	200 µg	200 µg	200 µg	200 µg	200 µg	200 µg	200 µg	200 µg	200 µg	200 µg	200 µg
Matching Placebo	P	P	P	P	P	P	P	P	P	P	P	P

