4.3. Method of Assigning Subjects to Treatment Groups

Eligible subjects meeting all study entry criteria will be randomly allocated in a 1:1:1 ratio to 1 of the 3 treatment groups.

The randomization schedule will be computer generated by using a permuted block algorithm and will randomly allocate the investigational produce (IP) to randomization numbers. The randomization numbers will be provided to the drug packager who will prepare blinded drug kits with all twelve (12) doses identified to maintain the drug blinding. The randomization schedule will be prepared by the sponsor or sponsor's representative before the start of the study. No one involved in the study performance will have access to the randomization schedule before official unblinding of treatment assignment. No subject will be randomized into this study more than once.

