7.3.2. Post-randomization

1. Measure vital signs (resting blood pressure, heart rate, respiratory rate, and oral body temperature) immediately before and 1 hour after the first dose of study drug on Day 0, then immediately before and 1 hour after the 24-hour and 40-hour doses, and at 48 hours.
2. Perform a 12-lead ECG before the first dose of study drug, and then at 90 minutes and 12, 24, and 48 hours after Time 0.
3. Pulse oximetry will be recorded at selected times, including baseline before Time 0 and at 90 minutes and 12, 24, and 48 hours after Time 0 (Tmax).
4. The subject is to record pain intensity (numerical rating scale) in the inpatient subject diary at Baseline before the first dose of study drug (Day 1). Thereafter, the subject is to record pain intensity and pain relief (5-point categorical scale) assessments at the following time points:
 - a. At 2.5, 5, 15, 30, and 45 minutes and 1, 1.5, 2, 3, 4, 5, 6, 7, 8, 12, 16, 20, 24, 32, 40 and 48 hours after Time 0, and immediately before each use of rescue analgesia.
 - b. At Early Withdrawal if a subject discontinues prematurely.
5. Administer the first dose of study drug within 9 hours (\pm 10 minutes) after the anesthetic block has been discontinued when a subject's pain intensity is ≥ 4 on the 11-point (0-10) NRS. Study drug will be administered from Time 0 through 48 hours within 10-minute windows.
6. Start stopwatches as soon as the first dose of study drug is administered. Stopwatches should be discontinued if the subject has not stopped them by the time of the second IP dose or first use of rescue medication (whichever occurs first).
7. Perform an oral cavity examination prior to and one hour after first dose.
8. Record concomitant medications.
9. Record AEs.
10. Subjects will complete a subject's global evaluation of study drug at the end of the treatment period (Day 3) before discharge from the study site or immediately before ET if a subject discontinues prematurely.
11. Dispense outpatient pain medication and an outpatient subject diary before discharge from the study on Day 3 (approximately 72 hours after completion of surgery).

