7.3 Handling of Missing Data

7.3.1 Handling of Missing Data for Efficacy Assessments

Use of Rescue Medication: Any pain intensity or pain relief score occurring within 4 hours after a subject has taken rescue medication for pain will be replaced by the last pain intensity or pain relief score prior to that use of rescue medication. If a second rescue medication for pain is used within that 4 hour duration, the pain intensity or pain relief scores from the time of the first rescue medication will be replaced by the assessment prior to the second rescue medication for the next 4

hours. The same method will be employed for a third and subsequent rescue medication.

Missing due to Dropouts: Missing values for pain intensity after a subject drops out of the study will be imputed as follows in the primary analysis:

- For SPID endpoints, the last available SPID (truncated SPID) will be used for analysis (e.g., if a subject dropped out after 32 hours of initiation of treatment, the truncated SPID calculated using timepoints up to 32 hours will be used as the post 32 hour timepoints like 40 hours and 48 hours).
- For TOTPAR endpoints, the last available TOTPAR (truncated TOTPAR) will be used for analysis
- For PID endpoints, the last available pain intensity will be used to impute the missing pain intensity and to calculate the PID

In addition, a sensitivity analysis using 1) missing as missing (i.e., no imputation) for dropouts and 2) multiple imputation will be performed for the primary endpoint to explore the impact of missing data after a subject drops out. The details of the sensitivity analysis are described in [Section 7.4](#).

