7.9.17 Time to First Use of Rescue Medication

Time to first use of rescue medication for pain is defined as the time from Time 0 to the first use of rescue medication. Rescue medications for pain will be identified by the sites on the Concomitant Medications eCRF. If rescue medication for pain is not taken, the time will be censored at the time of the last pain assessment.

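### Study drug is described both as scheduled every-4-hour treatment and as rescue medication; the two cannot both operate, and the SAP does not say that a study-drug dose is not rescue

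*Protocol*

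**What the plan says.** **Text that describes dosing by the clock**

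- The synopsis gives the active arms as 100 µg "every 4 hours [q4h] or 200" µg q4h, and Protocol 3.1 repeats the q4h arms.
- Protocol 1.4 bases dose selection on fixed daily totals: "For this study, the total daily doses of 600" µg and 1200 µg.
- Protocol 4.1, Table 1, fills all six slots on each of two days. Protocol 4.3 has "blinded drug kits with all twelve (12) doses identified to maintain the drug blinding".
- Protocol 7.3.2, item 5: "Study drug will be administered from Time 0 through 48 hours within 10-minute windows". Item 1 of the same section ties vital signs to a 24-hour and a 40-hour dose.
- Protocol 4.8, the rescue section itself, records rescue relative to the last scheduled study-drug dose.

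**Text that describes use on demand**

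- Protocol 3.1: "subjects will be allowed to use assigned study medication for primary rescue medication no more frequently than 4 hours from previous study medication dose", with a cap of six uses in 24 hours. The synopsis, Protocol 4.8 and SAP 2.2 say the same.
- Protocol 4.1 introduces Table 1 with "administered up to 6 doses per day as shown in the table below", which can be read as a ceiling.

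**Analysis text**

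- Under SAP 7.3.1, a score within 4 hours after rescue medication for pain "will be replaced by the last pain intensity or pain relief score prior to that use of rescue medication". No drug is named.
- SAP 7.9.16 counts rescue uses, again without naming drugs. SAP 7.9.17 says: "Rescue medications for pain will be identified by the sites on the Concomitant Medications eCRF".

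**The concern.** There are two linked problems.

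The first is the regimen. A site that follows Table 1 and Protocol 7.3.2 doses by the clock. A site that follows the permission in 3.1 and 4.8 could dose when the subject asks. Exposure is fixed in one case and depends on pain, and so possibly on treatment arm, in the other. The same skipped slot would be a deviation under one text and not under the other, which affects who enters the per-protocol population. SAP 2.4.2 anticipates about 30 and 15 subjects at two sites, so one site's reading would govern two thirds or one third of the 45 subjects.

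The second is the meaning of rescue in the analysis. SAP 2.2 attaches the rescue label to study drug, and SAP 7.3.1 overwrites scores after rescue without excluding study drug. Taken literally, the two would replace scores after active doses with scores from before them. The rescue endpoints would then count scheduled treatment as treatment failure.

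**Working it through.** **1. Reproduce the plan's own figures.** With one dose every 4 h: 24 / 4 = 6 doses a day, and 6 × 2 = 12 over 48 h (at 0, 4, 8, …, 44 h). Daily totals are 6 × 100 = 600 µg and 6 × 200 = 1200 µg. These match Table 1, the 12-dose kit and Protocol 1.4 exactly.

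**2. Compare with the permission.** It sets a minimum spacing of 4 h and a maximum of 6 in 24 h. The schedule in step 1 already uses every 4-hour interval and all six daily doses, so 6 − 6 = 0 slots remain. The permission therefore has effect only if dosing is as needed. In that case 600 and 1200 µg become maxima, and the 24-hour and 40-hour doses need not occur.

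**3. Check how the word rescue is used.** Immediately after the permission, Protocol 3.1 encourages subjects to wait at least 1 hour after the first dose before rescue. That cannot refer to study drug, which has a 4-hour minimum. SAP 7.9.11, 7.9.14 and 7.9.15 and Protocol 7.3.2 item 6 list the second dose and rescue use as separate events. The endpoint in SAP 3.1.2 measures time to rescue after each dose of study drug, which has little meaning if the doses are themselves rescue. SAP 7.9.17 finds rescue on the concomitant medication form. So SAP 2.2 disagrees with the rest of the SAP, and no sentence settles the matter.

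**4. Size the literal reading.** Inputs:

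- the 21 nominal times in SAP 7.9.5;
- the weights T_i − T_(i−1) in SAP 7.9.7, which sum to 48 h;
- the 4-hour replacement rule in SAP 7.3.1.

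Assumptions: dosing exactly every 4 h; dose 1 defines Time 0 and is not rescue; a score at a dose time is taken before that dose.

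| Reading | Time points replaced | Weight | Share of 48 h |
|---|---|---|---|
| Study drug is not rescue | 0 of 21 | 0 h | 0% |
| Doses 2–12 are rescue, strictly under 4 h | 3 of 21: 5, 6, 7 h | 1 + 1 + 1 = 3 h | 3 / 48 = 6.25% |
| Doses 2–12 are rescue, exactly 4 h included | 11 of 21: 5, 6, 7, 8, 12, 16, 20, 24, 32, 40, 48 h | 4 × 1 + 4 × 4 + 3 × 8 = 44 h | 44 / 48 = 91.7% |

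The wide gap arises because every assessment from 8 h onward falls on a multiple of 4 h, exactly one interval after a dose. With ±5-minute assessment windows (Protocol Table 2) and 10-minute dosing windows, individual points could fall on either side.

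**5. Rescue endpoints under the same label.** A subject taking all 12 doses has 12 − 1 = 11 rescue uses before any other analgesic is counted. Everyone who takes dose 2 is a rescue user, whatever the arm. Time to first rescue is at most about 4 h.

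**The case against.** The best defence is that the SAP's operative text already keeps study drug and rescue apart, as step 3 shows. Study drug is not ordinarily a concomitant medication, and exposure is summarised separately (Protocol 8.5.2, SAP 8.1.5). The reference to the concomitant medication form therefore points towards ibuprofen and ketorolac and away from study doses. That stands, and it makes 0% the likelier intent. It is still an inference from the name of a form, while SAP 2.2 says the opposite in words.

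Four stronger readings might be inferred, and the documents do not support them:

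- *Nearly the whole 48 hours would be lost.* This needs the less likely meaning of rescue and also the inclusive 4-hour boundary. Scores up to 4 h, and so SPID-4, are untouched in either case.
- *Scores are removed, so the overwritten share is the bias.* Scores are replaced, and Protocol 6.1.1 calls for an assessment just before each rescue use. From 8 h onward under exact 4-hourly dosing, one pre-dose score would generally replace another from about 4 h earlier. The share measures weight affected and gives no shift in SPID-48.
- *Subjects could exceed the planned exposure.* The permission carries the same spacing and daily cap as the schedule, so the maximum is unchanged. No passage states a minimum number of doses under on-demand use.
- *The two sites will behave differently.* Nothing shows this. Dosing is supervised by site staff, randomization is stratified by centre and site is in the model, so a site-wide habit would reach all arms there. A site term does not, however, correct for dosing that depends on each subject's pain.

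**Conclusion.** The regimen contradiction is direct and needs no assumption: scheduled 4-hourly dosing and study drug as rescue at 4-hour spacing cannot both operate. The passages must be reconciled, and which regimen applies is for the sponsor to decide.

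The analysis point is real but smaller. It is a conflict within the SAP and not a forecast of what the programmers will do. If the SAP 2.2 label were applied to the 7.3.1 rule, 6.25% to 91.7% of the SPID-48 weight would be overwritten with pre-dose scores, and the rescue endpoints would stop separating the arms. On the likelier reading the share is 0%. The range rests on exact 4-hourly dosing; under as-needed dosing it would vary by subject. It should be corrected because it touches the primary endpoint and a few sentences settle it.

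**What to change.** 1. Reconcile the synopsis, Protocol 3.1 and 4.8 with the q4h arms, Protocol 1.4, Table 1, 4.3 and 7.3.2, so that one dosing regimen is stated. The sponsor chooses which.
2. Remove or correct the sentence in SAP 2.2 that labels study drug as rescue, to match.
3. State in SAP 7.3.1, 7.9.16 and 7.9.17 that a study-drug dose is never counted as rescue medication. Define rescue for analysis as any non-study analgesic taken for pain after Time 0, including ibuprofen and ketorolac. A list limited to those two drugs would let any other analgesic taken for pain escape the replacement rule.
4. While editing 7.3.1, say whether a score at exactly 4 h is inside the window. The same boundary matters for genuine rescue.

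Cost: protocol wording, which Protocol 10.1 routes through a formal amendment with IRB approval, and a few SAP sentences before database lock and unblinding. No added assessments or subjects are needed.
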